#### **4 Background and Study Rationale**

Mild amounts of corneal astigmatism are often corrected at the time of cataract surgery with limbal relaxing incisions (LRIs), on-axis incisions or with low-cylinder powered toric IOLs. Leon P. et. al has shown that results from LRIs and toric IOLs significantly decreased refractive astigmatism, but Toric IOLs were more effective and predictable when compared to LRIs. One IOL available in Canada for the correction of mild corneal astigmatism is the enVista Toric IOL. The lowest available cylinder power for enVista Toric IOL is 0.9D. The goal of this retrospective study is to gain a better understanding of the postoperative outcomes in patients implanted with a low-cylinder powered toric IOL (enVista Toric 0.9D) vs non-toric IOLs (enVista).

#### **5 Study Objectives**

The primary objective of this study is to evaluate the performance of the enVista Toric 0.9D vs the enVista non-Toric IOL.

#### **6 Study Design and Methods**

##### **6.1 General Study Design**

The performance of the enVista Toric IOL will be compared with that of the enVista non-Toric (spherical) IOL. At least 384 eyes (n= 192 per lens type) from 3-4 Canadian centers will be investigated.

This is a retrospective chart review for preoperative and postoperative data conducted at least 4 weeks after IOL implantation.

##### **6.1.1 Total Number of Subjects**

The study will enroll at least 384 eyes presenting with at least 192 enVista Toric 0.9D IOLs and 192 enVista non-Toric (spherical) IOLs.

It is expected that the medical records of approximately 600 subjects will need to be evaluated in order to identify the required 384 eyes that are eligible for inclusion in this study.

#### **6.2 Study Population**

##### **6.2.1 Inclusion Criteria**

- Males and Females subjects age 18 or older on the date of the surgery
- Implant of enVista 0.9D Toric IOL or enVista non-Toric (spherical) IOL in at least one eye
- Data available at least 4 weeks after IOL implantation
- Eyes must qualify for the 0.9D toric lens based on the Barrett Toric Calculator (flipped axis must be less than 0.2D) (<https://ascrs.org/tools/barrett-toric-calculator>)
  - Study eyes were implanted with the 0.9D toric lens
  - Control eyes were not implanted with the 0.9D toric lens and implanted with a spherical (non-toric) equivalent instead

### **6.2.2 Exclusion Criteria**

- History of uncontrolled or clinically significant ocular comorbidities for the treated eye(s) before the surgery (e.g., dry eyes, retinal pathology, etc.)
- BCDVA of 20/25 or worse for the treated eye(s) after the surgery
- Excessive IOL rotation > 10 degrees (Toric IOLs only) for the treated eye(s) after the surgery

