## **8 Statistics**

### **8.1 Primary Effectiveness Endpoint**

The primary effectiveness endpoint is the mean reduction in cylindrical power of the eye. Reduction in the cylindrical power of the eye is defined as the difference between the magnitudes of the preoperative keratometric cylinder and the residual refractive cylinder (referenced to the corneal plane).

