### 8.4 Sample Size and Power

A sample size of 192 eyes in each group will have 90% power to detect a difference in means of 0.25 D assuming that the common standard deviation is 0.753 D using a two-group Satterthwaite t-test with a 2.5% one-sided significance level.

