## 9 Study Administration

### 9.1 Data Collection and Management

Paper source document worksheets will be created to capture all study related data. Data recorded in these worksheets will be entered into an electronic Case Report Form (Dacima eCRF) by qualified site personnel.

Access to the eCRF will be password restricted to designated and appropriately trained site personnel.

Subject identifiers will not be entered into the eCRF. Subjects will be identified by a subject number that will be sequentially assigned to each eligible medical record (i.e., subject).

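### Excluding only toric eyes that rotated more than 10 degrees after surgery biases the primary comparison toward the toric lens, by an amount the plan gives no means of determining

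*Combined protocol and SAP*

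**What the plan says.** Two exclusions in Section 6.2.2 depend on what happened after the operation. One applies to the toric arm alone: "Excessive IOL rotation > 10 degrees (Toric IOLs only) for the treated eye(s) after the surgery". The other applies to both arms: "BCDVA of 20/25 or worse for the treated eye(s) after the surgery".

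Section 8.1 bases the primary endpoint on "the difference between the magnitudes of the preoperative keratometric cylinder and the residual refractive cylinder", and Section 8.2 tests in one direction, with a larger toric mean as the alternative. Section 5 sets the aim broadly: "The primary objective of this study is to evaluate the performance of the enVista Toric 0.9D vs the enVista non-Toric IOL". It does not limit the question to lenses that stayed in position.

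Section 8.3 plans a single comparison, a two-sample t-test, with no second analysis set and no sensitivity analysis. Section 7.4 collects rotation for toric lenses only where the chart has it. Under Section 9.1, "Subjects will be identified by a subject number that will be sequentially assigned to each eligible medical record". Section 6.1.1 expects about 600 subjects' records to be evaluated to find 384 eyes, but does not divide the remainder by arm or reason.

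**The concern.** Eligibility should rest on what was known before or at implantation. Here a toric eye is removed because the toric correction did not hold its axis, and that is part of how the lens performs. The removed eyes are, on average, those with the poorest values of the primary endpoint. No control eye is removed for a comparable reason, and none could be, because turning a spherical lens does not change cylinder. Adding a control criterion would therefore not help. The fault is conditioning on a postoperative event specific to one treatment.

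As written, the result would describe toric lenses that stayed within 10 degrees but would be reported as the performance of the toric lens. The error runs in the direction of the study hypothesis. With no count of exclusions by arm, a reader could not tell whether it is trivial or material. Numbers go only to eligible records, so an eye dropped under this rule need not be recorded anywhere in the study data.

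The acuity exclusion also conditions on an outcome, but it is a lesser matter. It applies to both arms, its net direction is undetermined, and it mainly narrows the population.

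**Working it through.** **Inputs from the documents.** Section 8.4: 192 eyes per arm, difference 0.25 D, "assuming that the common standard deviation is 0.753 D using a two-group Satterthwaite t-test", one-sided 2.5% level, 90% power. Section 4: "The lowest available cylinder power for enVista Toric IOL is 0.9D"; the plane of that power is not stated. The documents give no rotation rate, no distribution of rotation and no outcomes for rotated eyes.

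**1. The plan's own figure.** By the noncentral t distribution, 192 per arm gives 90.06% power and 191 gives 89.91%, so 192 is the smallest sufficient number. The sample-size calculation is correct. The planned standard error of the difference is 0.753 × √(2/192) = 0.0769 D.

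**2. Direction.** Let K be the corneal cylinder, C the lens cylinder at the corneal plane and θ the rotation from the intended axis. For a lens planned on the corneal axis, residual cylinder is R(θ) = √(K² + C² − 2KC·cos 2θ). Cos 2θ falls steadily from 0 to 90 degrees, so R rises throughout, whatever K and C are.

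With error in the planned axis, a single eye can improve by chance. A simulation used C = 0.9 D, K uniform on 0.4-1.3 D, rotation of 10-30 degrees either way, and axis error with SD 0 to 30 degrees. The mean loss from rotation stayed positive, falling from 0.42 D to 0.11 D as axis error grew, while 0% to 37% of single eyes improved. The direction therefore holds for the mean, which is what the test compares.

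**3. Size.** Let p be the fraction of toric eyes removed, and d their mean shortfall in cylinder reduction relative to the retained toric eyes, whose mean is m. The all-eyes mean is (1 − p)m + p(m − d) = m − pd, so the bias is pd.

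To give d a scale, take R(θ) minus its average over retained rotations of 0-10 degrees (uniform, assumed), with K and C each 0.6-0.9 D (assumed):

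| Rotation of removed eyes | Shortfall d |
|---|---|
| 12° | 0.10-0.22 D |
| 15° | 0.15-0.31 D |
| 20° | 0.25-0.46 D |
| 25° | 0.36-0.60 D |

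Bias for assumed p and d. The last column is the true one-sided rejection rate if the all-eyes difference were zero:

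| p | d | Bias pd | Bias / 0.0769 | Rejection rate |
|---|---|---|---|---|
| 1% | 0.30 D | 0.003 D | 0.04 | 2.7% |
| 5% | 0.45 D | 0.0225 D | 0.29 | 4.8% |
| 10% | 0.60 D | 0.060 D | 0.78 | 12% |

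If the removed eyes had turned only about 15 degrees, the bias would run from 0.01 × 0.15 = 0.0015 D to 0.10 × 0.31 = 0.031 D.

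At d = 0.45 D, the bias reaches a quarter of a standard error at p = 0.25 × 0.0769 / 0.45 = 4.3%, and half at p = 0.5 × 0.0769 / 0.45 = 8.5%.

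**4. What the screening figure can tell us.** Nothing useful. If all 600 − 384 = 216 surplus records were rotated toric eyes, p would be 216/(192 + 216) = 53%, which bounds nothing in practice.

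**5. Effect of keeping the eyes.** Per 192 retained toric eyes, 192p/(1 − p) would be added: 1.9 at p = 1% and 21.3 at p = 10%. Taking 0.753 D as the SD within both retained and rotated eyes (assumed), the toric SD becomes √(0.753² + p(1 − p)d²). At p = 10% and d = 0.6 D this is √(0.5670 + 0.0324) = 0.774 D.

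**The case against.** The strongest reply is that the rule is openly stated and may simply define the population. If the aim were the effect of a toric lens that stays aligned, excluding rotated eyes would limit generalisability and would not be a bias. That estimand could be legitimate, but Section 5 does not state it, and Section 4 speaks of outcomes in patients implanted with the lens. On the objective as written, the objection does not succeed.

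The second reply concerns size, and much of it stands. The rate and the shortfall are both assumed. A shortfall of 0.3-0.6 D corresponds roughly to rotation of 20-25 degrees, whereas the rule begins just above 10. The upper figure of 0.78 standard errors needs both extremes at once, and error in the planned axis would reduce the loss. These points limit what can be said about materiality but leave the direction of the mean unchanged.

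Third, because Section 7.4 collects rotation only where available, some rotated eyes may go unrecognised and stay in. That may shrink the bias, and it also makes its size harder to know.

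Finally, the plan does not forbid a screening log and the charts remain, so the excluded eyes might be recoverable. The supportable statement is that the plan provides for no such count. Counting alone, with a sensitivity analysis that adds the rotated eyes back, would let readers judge the size, but the primary estimate would still answer a narrower question than Section 5 asks.

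**Conclusion.** The concern holds and should be fixed. The rule removes toric eyes alone, on a postoperative failure that on average worsens the primary endpoint, and so favours the alternative hypothesis. The direction follows from the endpoint definition.

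The size cannot be derived from the documents. Under the assumed 1-10% removed and 0.3-0.6 D shortfall, it is between 0.003 and 0.06 D, against a design difference of 0.25 D: about 1% (0.003/0.25) to 24% (0.06/0.25) of it. It would be smaller if removed eyes lie only slightly beyond 10 degrees or if axis planning is imprecise, and negligible if rotation is rare. The sample-size calculation is not in error.

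**What to change.** - **Primary analysis:** include every eye that meets the preoperative criteria and has refraction at 4 weeks or later, whatever its postoperative rotation.
- **Sensitivity analysis:** repeat the comparison without toric eyes rotated more than 10 degrees, labelled as such. State in advance how toric eyes with no recorded rotation are handled.
- **Acuity rule:** run the comparison with and without the postoperative BCDVA exclusion, naming the primary version in advance.
- **Reporting:** give the number of eyes affected by each postoperative rule, by arm, and summarise device-related adverse events on all eyes that meet the preoperative criteria. Assign a subject number and a record to those eyes so that they can be counted.

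**Cost.** The protocol and SAP wording must change, and eyes now screened out must be abstracted. For rotation this is about 2 to 21 toric eyes per 192 retained, under the assumed 1-10%. The number added under the acuity rule cannot be estimated from the documents. The toric estimate may become less favourable, and the toric SD could rise from 0.753 D to at most about 0.774 D under the same assumptions. The aligned-only result is still reported.

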## **7 Study Procedures**

### **7.1 Date Range of the study**

Cases will be included in the study if they received an initial enVista IOL on or after 01-Sep-2018.

### **7.2 Subject Selection**

Eligibility will be determined and confirmed at each site by the site Investigator.

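### Site investigators judge eligibility with outcomes already on file, and the plan states no closing date, all-eligible rule, order of review or count of exclusions

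*Combined protocol and SAP*

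**What the plan says.** All references are to the combined protocol and SAP.

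- **Design (6.1).** "This is a retrospective chart review for preoperative and postoperative data conducted at least 4 weeks after IOL implantation". Allocation to lens is whatever happened in practice.
- **Who selects (7.2).** The section is a single sentence: "Eligibility will be determined and confirmed at each site by the site Investigator".
- **Window (7.1).** "Cases will be included in the study if they received an initial enVista IOL on or after 01-Sep-2018". No end date follows.
- **Number (6.1, 6.1.1).** "The study will enroll at least 384 eyes", at least 192 per lens type, with the expectation that "approximately 600 subjects will need to be evaluated in order to identify the required 384 eyes that are eligible".
- **Postoperative exclusions (6.2.2).** "BCDVA of 20/25 or worse for the treated eye(s) after the surgery", which applies to both arms, and "Excessive IOL rotation > 10 degrees (Toric IOLs only) for the treated eye(s) after the surgery".
- **Preoperative criteria (6.2.1, 6.2.2).** Eyes in both arms must qualify for the 0.9D toric on the Barrett calculator, with a flipped-axis value below 0.2D. Eyes with uncontrolled or clinically significant ocular comorbidity are excluded, with examples rather than a closed list.
- **Sources and numbering (7.3, 9.1).** Charts and EMR systems are used to find matching participants. Subject numbers are given in sequence to eligible records.
- **Abstraction (7.4).** Keratometry with axis, SIA, incision angle and IOL power are taken for all eyes. Predicted residual cylinder and axis are taken for toric eyes only. No field holds the calculator qualification or the flipped-axis value in either arm.

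**The concern.** In a prospective trial, the set of eyes is fixed before anyone can know the result. Here the result is already in the chart, so the protection has to come from a written rule that leaves no choice about which eyes enter. The eligibility criteria say who may enter. They do not say whether all such eyes do, over what closed period, or in what order the chart is read.

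The consequence would be selection related to the outcome and differing by lens type. The analysis could not repair it. An eligible eye that was passed over never reaches the data set, and the by-treatment summaries in 8.3 cannot show it. The same holds for an eye removed under a comorbidity judgement made by someone who had already seen the refraction. If rejected charts are not counted, a reader of the report cannot judge whether this happened.

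**Working it through.** **1. The plan's own figure.** Inputs from 8.4: 192 eyes per group, SD 0.753 D, difference 0.25 D, one-sided 2.5%.

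- SE of the difference = 0.753 × √(2/192) = 0.0769 D.
- Noncentrality = 0.25 / 0.0769 = 3.25, with 382 degrees of freedom and critical t = 1.966.
- Power = 90.1%, which agrees with the stated 90%.
- Smallest observed difference that rejects H0 = 1.966 × 0.0769 = 0.151 D.

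The sample size is sound. The issue is which eyes fill it.

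**2. What fixes the set of eyes.**

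| Question | Section | What is stated |
|---|---|---|
| First surgery date | 7.1 | 01-Sep-2018 |
| Last surgery date | 7.1 | Nothing |
| Number of eyes | 6.1, 6.1.1 | A minimum; no maximum and no stopping rule |
| Who decides | 7.2 | The site investigator |
| Order of review | 7.2, 7.3 | Nothing |
| Are all eligible eyes taken? | 7.1, 7.3, 9.1 | Compatible with yes; not stated |
| Are rejected charts counted? | 9.1 | Nothing; only eligible records are numbered |

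**3. Whether the outcome is in view.** Postoperative BCDVA (both arms) and rotation (toric arm) must be read to apply 6.2.2. The postoperative manifest refraction is abstracted from the same medical records (7.4). The endpoint in 8.1 and 8.3 is preoperative keratometric cylinder minus postoperative refractive cylinder at the corneal plane. The person confirming eligibility therefore works from a record that holds both parts of the endpoint.

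**4. Where judgement enters.** Age, surgery date, lens type, the BCDVA cut and the rotation cut are fixed by a number or a fact. The comorbidity exclusion is not, because it turns on what is clinically significant. The calculator criterion has a threshold, but the value compared with it is not recorded.

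**5. How it would reach the result.** Write b_T and b_C for the shift in mean reduction that selection causes in each arm. The t-test in 8.3 uses no covariates, so it estimates

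(μ_T + b_T) − (μ_C + b_C) = (μ_T − μ_C) + (b_T − b_C).

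A shift common to both arms cancels. A shift that differs by lens type enters in full, in either direction. The documents contain nothing from which b_T − b_C could be estimated.

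**6. The calculator criterion.** Section 6.2.1 applies it to both arms and uses it to make them comparable. Section 7.4 records its result in neither.

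**The case against.** The best answer is that the plan already implies taking every eligible eye. Section 7.1 says cases will be included if they meet the date. Section 7.3 uses records to find participants who match the criteria. Section 9.1 numbers the eligible records. With no upper limit, nothing tells a site to choose. This is a natural reading and it stands as such, so the plan cannot fairly be said to permit picking. What remains is that no section says it, and the phrase in 6.1.1 about finding the required number can equally be read as filling a target.

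It can also be said that the window closes in practice, since data at least 4 weeks after implantation must exist (6.1, 6.2.1). That is right, and the set is not boundless. But the abstraction date it depends on is not fixed in advance.

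Three stronger conclusions are tempting, and the documents do not support them.

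- **That many eligible eyes will be discarded.** From 6.1.1, 600 − 384 = 216 records (36%) would go unused with one eye per subject, or 600 − 192 = 408 (68%) with two. Section 6.1.1 describes the expected yield of eligible eyes, so these charts may simply be ineligible. The figures are not evidence of selection.
- **That the error rate is inflated by a known amount.** Assumed shifts of 0.05, 0.10 and 0.15 D favouring toric would give a one-sided error of about 9.5%, 25% and 49%. The same shifts against toric would cut power at 0.25 D to about 74%, 49% and 25%. No section supports any of these shifts or a direction, so they carry no weight in the conclusion.
- **That control eligibility in particular can be re-checked only in part.** The documents do not list the calculator's inputs, so whether the abstracted data suffice cannot be decided from them. Toric eyes lack a qualification field too. The predicted cylinder recorded only for toric eyes is not used in the primary endpoint or test.

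**Conclusion.** The point holds as a gap in the selection procedure. The omissions are certain from the text: no closing date, no stated all-eligible or consecutive rule, no order of review, no count of exclusions, and no record of the calculator result in either arm. They go beyond missing detail because the person judging eligibility can see the outcome, one exclusion is a matter of judgement, and the primary test makes no adjustment.

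Whether bias would follow is not known, nor is its size or direction. It requires either choice among eligible charts or outcome-aware use of the comorbidity exclusion, and an effect that differs between lens types. The documents establish neither. The plan should be changed because the remedy is cheap and cannot be applied credibly once the charts have been chosen.

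**What to change.** **In 7.1 and 7.2**

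- Set one closing date that applies to both lens types at each site, and include all consecutive eligible eyes from 01-Sep-2018 to that date. A common date is better than filling a number for each lens, which could end at different times and put the arms in different calendar periods.
- Determine and record the preoperative and calculator criteria before opening postoperative data. Then apply the existing postoperative exclusions unchanged.
- Keep and report counts of charts reviewed and excluded, by lens type and reason.

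**In 7.4**

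- Record the calculator qualification and flipped-axis value for every eye in both arms. They are already needed to apply 6.2.1.

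**Cost.** Protocol wording, a simple log and a few eCRF fields. Sites lose freedom in choosing charts, and more than about 600 records may need review. The fixed order cannot mask an investigator who already knows the outcomes. It sets the sequence and leaves a record that a reader can check.

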### **7.3 Data Sources**

Sources of data include paper medical records and/or EMR systems. Such medical records and systems will be used in order to identify participants who match study defined eligibility criteria.

### **7.4 Variable Abstraction**

The following clinical endpoints to be collected from subject's medical records:

- Subject Demographics and Medical History
  - Include lens calculation data: IOL power selected, predicted residual spherical equivalent refraction, surgically induced astigmatism (SIA), incision angle.
  - If toric IOL: Also include predicted residual cylinder and axis, target axis of placement, and actual axis of placement
- Keratometry (K steep/K flat with axis): Preoperative and Postoperative
- Manifest Refraction (sphere/cylinder/axis): Preoperative and Postoperative
- UCDVA: Preoperative and Postoperative
- BCDVA: Preoperative and Postoperative
- IOL Rotation: If available, also include actual vs. target (Toric IOLs only)
- The presence of any device related adverse events.

## **8 Statistics**

### **8.1 Primary Effectiveness Endpoint**

The primary effectiveness endpoint is the mean reduction in cylindrical power of the eye. Reduction in the cylindrical power of the eye is defined as the difference between the magnitudes of the preoperative keratometric cylinder and the residual refractive cylinder (referenced to the corneal plane).

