### 8.3 Statistical Methods

Continuous variables will be summarized by treatment using the sample size, mean, standard deviation, minimum, and maximum. Categorical variables will be summarized by treatment using frequencies and percentages. Missing data will not be imputed.

The preoperative keratometric cylinder (D) will be calculated as the difference between the preoperative steep and flat keratometric powers (both in diopters). The postoperative manifest refraction cylinder (PMRC) will be referenced to the corneal plane assuming a vertex distance of 13 mm as follows.

$$PMRC = \left| \frac{1000(Sph + Cyl)}{1000 - 13(Sph + Cyl)} - \frac{1000 Sph}{1000 - 13 Sph} \right|$$

Where:

- PMRC = the postoperative manifest refractive cylinder at the corneal plane (D)
- Sph = the postoperative manifest refraction sphere at the spectacle plane (D)
- Cyl = the postoperative manifest refraction cylinder at the spectacle plane (D)

Reduction in the cylindrical power of the eye (D) will be computed as the preoperative keratometric cylinder minus the PMRC and summarized using continuous summary statistics by treatment. The statistical hypotheses will be tested using a two-sample t-test assuming unequal variances. If the one-sided p-value is less than 0.025 (or, equivalently, the two-sided p-value is less than 0.05 and the treatment difference is greater than zero), then the null hypothesis will be rejected and the toric IOL will be statistically successful in this outcome. A two-sided 95% confidence interval around the treatment difference will be reported.

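### Does leaving the endpoint refraction without a named visit undermine the primary comparison?

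*Combined protocol and SAP*

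**What the plan says.** Section 8.1 defines the endpoint as "the difference between the magnitudes of the preoperative keratometric cylinder and the residual refractive cylinder (referenced to the corneal plane"). Section 8.3 computes the second term from the postoperative sphere and cylinder, the latter described as "the postoperative manifest refraction cylinder at the spectacle plane (D"). Neither section names a visit, a window or a rule for choosing among several refractions. Section 7.4 lists the item as "Manifest Refraction (sphere/cylinder/axis): Preoperative and Postoperative" and names no surgery date or refraction date.

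Timing appears in two other places. Section 6.1 states: "This is a retrospective chart review for preoperative and postoperative data conducted at least 4 weeks after IOL implantation". Section 6.2.1 requires: "Data available at least 4 weeks after IOL implantation". Neither sets an upper limit. Section 7.1 opens the surgery window and gives no closing date: "Cases will be included in the study if they received an initial enVista IOL on or after 01-Sep-2018".

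The acuity exclusion in Section 6.2.2, "BCDVA of 20/25 or worse for the treated eye(s) after the surgery", also names no visit, and nor does the rotation exclusion beside it. Under Section 9.1, site personnel enter the data from worksheets. Under Section 9.3, the link to subject identifiers is destroyed once the data have been cleaned and analysed.

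**The concern.** A primary endpoint normally states when it is measured. Here an eye may have more than one refraction after week 4, and the text does not say which one counts. Abstraction takes place at 3-4 centres from charts that show both the lens implanted and the result. If the more favourable reading were taken more often for toric eyes, the treatment difference would be biased towards success and the planned t-test could not reveal it. Without dates in the listed data, follow-up time could not be compared between lenses, and once the identifier link is gone the charts could not be traced.

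Two related worries follow. An eye whose corrected acuity crosses the Section 6.2.2 threshold between visits is in or out depending on the visit read. And if the data required by Section 6.2.1 need not include a refraction, then, with no imputation under Section 8.3, 192 enrolled eyes per group might give fewer than 192 analysable eyes.

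**Working it through.** **1. The plan's own figure.** Inputs from Section 8.4: 192 eyes per group, difference 0.25 D, common SD 0.753 D, one-sided 2.5%.

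- SE of the difference = 0.753 × √(2/192) = 0.0769 D.
- Noncentrality = 0.25/0.0769 = 3.25, df = 2 × 192 − 2 = 382, critical value 1.966.
- Power = 90.1%. The stated 90% reproduces, and nothing in this point alters the sample size.

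**2. What the timing text settles.** Section 6.2.1 attaches the 4 weeks to the data. Section 6.1 uses the same interval in a sentence about preoperative and postoperative data. Taken alone, the Section 6.1 sentence could be dating the chart review. Beside Section 6.2.1, the natural reading is that postoperative data come from week 4 onwards. Early refractions are therefore out. What stays open is the choice when a chart holds more than one later refraction.

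**3. Same handling in both arms.** If the same rule, or the same looseness, applies to both lenses, any shift in the group means cancels in the difference. The shift is 0 and the type I error is 2.5%. This covers even an optimistic habit: taking the better of two readings in both arms, with 25% of eyes having two, raises each group mean by about 0.03-0.04 D but leaves the contrast alone.

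**4. Different handling by lens.** The documents give neither the share of eyes with two refractions (f) nor the within-eye SD (SDw). Assume f = 0.10-0.25 and SDw = 0.20-0.30 D. Let k be the share of two-refraction toric eyes in which the better reading is taken, with no such selection in controls. The expected gain from the better of two normal readings is SDw/√π = 0.564 × SDw, so

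shift = 0.564 × SDw × f × k,

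and type I error = P(noncentral t, df 382, noncentrality shift/0.0769, exceeds 1.966).

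| k | f | SDw (D) | Shift (D) | Share of 0.25 D | One-sided type I error |
|---|---|---|---|---|---|
| 0.5 | 0.10 | 0.20 | 0.0056 | 2% | 2.96% |
| 0.5 | 0.25 | 0.30 | 0.0212 | 8% | 4.60% |
| 1 | 0.10 | 0.20 | 0.0113 | 5% | 3.49% |
| 1 | 0.25 | 0.30 | 0.0423 | 17% | 7.92% |

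These rows show what one-sided selection would do. They do not bound the effect, because f, SDw and the limit of two refractions per eye are all assumed. Larger inputs would give larger shifts.

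**5. Analysable eyes.** If 5-10% of the 192 eyes per group lacked a qualifying refraction (assumed), 182-173 would remain. The SE becomes 0.0789-0.0810 D and power 88.5-86.8%. Sections 6.1 and 6.1.1 set the 384 eyes as a minimum, so a shortfall can be made up within the plan.

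**6. Whether the choice can be recovered.** Sites must know the surgery date to apply the age criterion in Section 6.2.1 and the date limit in Section 7.1. Section 9.3 removes the identifier link only after cleaning and analysis, and keeps subject records for at least 2 years. The worksheets and the eCRF of Section 9.1 are not among the documents, so the absence of dates from the Section 7.4 list does not show that dates go uncaptured.

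**The case for a change.** The strongest case for a change is that this is the primary endpoint of an unmasked retrospective study. No passage gives site staff a free choice of refraction, but none removes it either. The 4-week floor excludes early readings without choosing among later ones, and with surgeries from September 2018 and no upper limit, follow-up may vary widely. The dataset as listed would not show which visit was used. The Section 6.2.2 exclusions carry the same ambiguity. The remedy is cheap: one selection rule, two date fields and no new visits.

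Most of this stands as description. The selection rule is unwritten, the dates are not listed, and stating them would improve the document. What does not stand is the step from an unwritten detail to a faulty analysis. That staff would choose by lens or by result is an inference, as is the claim that the choice could not be reconstructed. No rule in the plan yields a wrong result, and the inflated error rates need selection in one arm only, which nothing in the documents indicates. Reading the data requirement in Section 6.2.1 as excluding the refraction is possible but strained, since the refraction is the only postoperative measurement in the endpoint.

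**Conclusion.** The gap is real but narrow: the plan does not say which manifest refraction at or after week 4 supplies the endpoint when a chart holds several. It is missing operational detail of a kind that a worksheet or a data-handling note would sensibly fill, and it does not require a change to the design, test or sample size. The effect on the treatment difference is zero if both lenses are handled alike. Otherwise it cannot be quantified from the documents; the illustrated 0.006-0.042 D rests wholly on assumed shares, an assumed within-eye SD and assumed selection in the toric arm alone. As a clarification only, it would help to name one rule for both lenses, say which visit the postoperative exclusions refer to, and record the surgery and refraction dates so that follow-up time can be reported by lens. This conclusion assumes that the 4-week floor applies to the refraction and that abstraction follows one practice for both lenses.
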